1 BACKGROUND

As the world makes progress on reducing infectious diseases and other drivers of premature mortality, non-communicable diseases (NCDs) such as diabetes, hypertension, and cardiovascular diseases have come to account for over 70% of deaths worldwide¹. High and middle income countries in particular have faced rapidly rising burdens of NCDs, as improving social conditions and advanced medical treatments enable their populations to survive into old age. In these populations, co-occurrence of multiple chronic illness, also known as multi-morbidity, is also growing. These shifts in population health imply major new demands on the health system, as patients with multiple chronic conditions typically require more care, from multiple levels of the health system, over extended periods of time. One response to this challenge in the US and Europe has been a move towards more proactive and comprehensive primary care models for complex patients. These models include more proactive care by primary care providers and their team, and greater efforts to coordinate care for patients based on their specific needs for specialist care, nursing care, preventive care, improved coordination around care transitions, and greater attention to social and economic needs of patients.

Estonian policymakers have developed a model to improve primary care, known as Enhanced Care Management (ECM). ECM program components include physician coaching, risk stratification, co-creation of care plans, and proactive follow up with patients between visits and after hospitalizations, and coordination with social services when applicable for patient. ECM's theory of change is that through sustained coaching, physicians can provide better care by following this model. With better management of chronic care conditions, patients will increase their appropriate use of primary health care services, and will have reduced need for secondary and tertiary services for ambulatory-care sensitive conditions. Over time, this improved care should result in improved health and quality of life for patients, and increased patient satisfaction with care.

This protocol presents a pre-analysis plan for the evaluation of the Estonian Enhanced Care Management program.

Setting

Estonia's health system faces growing challenges with population aging and growing burden of NCDs. As of 2017, approximately 50% of the population was above the age of 44 and 50% of the total population had at least one chronic illness. Among those aged 0-18, 18.2% had at least one chronic illness and 3.4% had multiple chronic illnesses, while for those over 45, 65.6% had at least one chronic illness and 71% had multiple chronic illness. Notably, mortality rates for cardiovascular and circulatory system diseases are much higher than in comparator EU countries, and Estonia has among the higher rates of avoidable hospital admissions in the EU².

ECM Intervention

The Enhanced Care Management (ECM) intervention consists of training and coaching family physicians and their teams to develop holistic care and pro-active outreach plans for chronically ill patients or those vulnerable to developing chronic illnesses. The core goal of ECM is to improve the quality of care provided to complex patients, including by increasing the use of preventive care, improving coordination of care across health system levels, and increasing patient involvement in care. These elements can improve patient health and quality of life, and may reduce the need for curative medical services—for example, by supporting patients with type 2 diabetes to improve their diet and increase physical activity to limit further deterioration in their health.

ECM practices include improved tracking of tests and referrals, follow-up by PHC providers after hospital discharges, tracking of medication adherence, monitoring of patients between clinic visits, and greater focus on clinical quality. It includes

four elements: identifying high-risk patients through risk stratification, developing care management plans by the primary care physician in consultation with the patient, proactively linking care providers together, and developing a team approach between patients and their caregivers.

2. METHOD AND DESIGN

2.1 ECM IE Design Overview

This study incorporates a two stage randomization, first at the clinic level and second at the patient level.

2.2 Clinic randomization

EHIF identified 421 clinics (786 providers) who were eligible for the ECM program. The study team then excluded clinics which had participated in the pilot study, those not currently operational, as well as clinics with five or more practicing providers. From the remaining 546 clinics, we conducted a stratified sampling via coarsened exact matching with two quality of care measurement indicators – the practice’s Quality Bonus Scheme (QBS) score and a management score given to each clinic³. We grouped all the clinics into blocks of similar performance based on the QBS and management score. From each performance block, we randomly selected one-fourth of the clinics into ECM program.

This sampling resulted in 144 providers randomly selected into ECM and 402 providers in the control group. All providers in randomly selected clinics were enrolled in ECM. After the clinic randomization and after providers were invited to join the ECM program, 47 providers have refused or dropped out. The most common reasons given were lack of time, or other logistical issues, or in some cases health problems with several providers themselves. Since these providers dropped out of the program before the patient classification began, their patient population is excluded from randomization into the program..

2.3 Patient randomization

The next stage of randomization was conducted at the patient level. From each participating ECM provider, 25 patients were eligible for selection into the ECM program. (This number was based on EHIF's budgetary limitations for the program). Each year, EHIF's algorithm uses their Mini Information System Portal (MISP) to update the list of at-risk patients who have multiple chronic illnesses. For this project, the providers selected in the ECM group evaluated these patients and assigned an additional risk score to each of the patients identified in MISP, as follows:

- 1-Mild/moderate risk of deteriorating health
- 2-Severe risk of deteriorating health

Given the mix of mild/moderate and severe patients within each provider, we conduct a stratified random sampling of patients into ECM based on the risk classification, such that every patient within each risk classification group has equal probability of selection, and there are at most 25 patients selected into the ECM program from each provider. All the patients within every provider are stratified into two strata – one for mild/moderate risk and second for severe risk. From each strata we then randomly selected patients into the treatment proportional to their share in the strata with a maximum of 25 patients selected in treatment. Five providers had identified fewer than 25 patients who had a risk of deteriorating health. For these providers, all the patients were assigned to treatment. The patients assigned to ECM were invited to join ECM by their providers; all patient acceptances and refusals are recorded in their electronic health records which will be shared with the research team during the analysis phase.

2.4 Data

2.4.1 Provider Sample

EHIF has a network of approximately 800 primary care providers (family physicians), roughly 70% of whom work in a solo practice clinic⁴. The research team was provided with a dataset of all the clinics, linked providers, with their annual QBS score. This was the basis for construction the sampling frame for the provider randomization.

In order to construct performance blocks for randomization, we used the QBS data and management scores for 2019. QBS is Estonia's performance-based incentive program. We constructed a need- adjusted QBS score re-weighting each indicator based on the experience of the scheme, awarding proportional credit to providers at an indicator level and adjusting the coverage rates for providers based on the patient need⁵. The management score is a sum of points awarded on 15 indicators about the clinic's working and managerial practices. The average score per clinic on management indicators is 10 and the average need-adjusted QBS score per clinic is 306. Because the management score was only available at the clinic level, we average the QBS score for the clinic for sampling.

2.4.2 Patient Sample

EHIF's Mini Information System Portal (MISP) is the portal used by EHIF to list patients who have multiple chronic illnesses, and contains information such as the patient's family physician, and the number of co-morbidities. We matched this dataset to the list of ECM providers, to generate lists of higher-risk patients. Additionally, every ECM provider gave an additional risk score (mild/moderate or severe risk) to each of the patients in MISP.

2.1.1 EHIF billing data

For all the data on the outcomes such as health care utilization, provider management of tracer conditions and markers of quality of care we use longitudinal digitized billing records. This data includes every health system interaction for Estonian citizens covered by EHIF. We have electronic billing records spread over eight health care services categories - primary health care, day care, outpatient care, outpatient nursing care, outpatient rehabilitation care, inpatient care, inpatient nursing care, and inpatient rehabilitation care over a 10 year period (2009 until 2019). Each dataset contains three elements. First, every care type contains a claims summary dataset, identified by a bill number. These are initiated by the provider after every episode of care. This data includes the duration of a treatment, type of care, and physician and patient details in reference to the care episode. Second, claims summary dataset is accompanied by a diagnosis dataset that describes all the diagnosis which were relevant to the given care episode. Finally, the third accompanying dataset is the procedures dataset that describes all the medical procedures that were conducted within a given episode of care. We have the billing record containing the associated single insurance payer insurance fund claims, the diagnosis and treatment for each claim filed. In each of these claims we use the International Classification of Disease (ICD) codes of diagnoses, and the procedures.

All the key outcomes of this study will utilize these systems of data, de-identified in compliance with Health Insurance Portability and Accountability Act (HIPAA) regulations.

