2.3 Outcomes

Given these hypotheses, we focus on three outcome domains: overall healthcare utilization, provider management of tracer conditions, and measures of PHC-sensitive acute care. In domains one and three, we highlight 3 primary outcomes below; the remaining indicators are all secondary study outcomes.

- 1. *Healthcare utilization*: This outcome will be continuous and measures the following indicators during the intervention year, at the patient level:
 - number of primary health care interactions (**primary outcome**)

- number of inpatient care interactions (hospitalizations) (**primary outcome**)
- number of outpatient (ambulatory) services (**primary outcome**)
- number of inpatient post-hospitalization services (nursing and rehabilitation)
- number of outpatient post-visit services (nursing and rehabilitation)
- number of follow up by telephone
- number of follow ups due to chronic illness

- 2. *Provider management of tracer conditions:* This outcome measures provider compliance with Domain II QBS standards as the measure of quality care provision. The QBS has a set of guidelines for monitoring outlined for managing type 2 diabetes (ICD10 E11), hypertension (ICD10 I12-115) and myocardial infarction (ICD10 I21-I23, I25.2). This outcome measures the share of patients who are managed in compliance with the guidelines for monitoring, out of the total number of patients who have a diagnosis of the three conditions in the intervention year aggregated at the provider level. The guidelines for each condition are described in **Table 1**.

Example outcomes for this domain include:

- For type-2 diabetes: monitoring of glycosylated Hb (HbA1C), creatinine, cholesterol level (1 per year).
- For hypertension high risk patients: monitoring of cholesterol level, cholesterol fractions, glucose/glycosylated Hb, creatinine (1 per year); counselling and appointment with family nurse (per year).
- For myocardial infarction patients: Monitoring of cholesterol level (1 per year), glycosylated Hb (HbA1C) (1 per year), counselling with family nurse (1 per year).

Table 1. QBS Compliance Guidelines

Category	Indicator	Description	Measurement
Diabetes - type II	Monitoring	Glycosylated hemoglobin	1 per year
		Creatinine values	
		Cholesterol values	1 per 3 years
		Cholesterol fraction values	
		Counselling for chronic patient	1 per year
Diabetes - type II	Medication	Prescribed for all diabetes type-II patients	6 prescriptions in 14 months

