2.4 Statistical model

For outcome (1) and (3), we specify the difference in means in the intervention year using the below specification:

$$Y_{ikt} = \alpha + \beta(ECM_i \times Post_t) + \gamma_1 ECM_i + \gamma_2 Post_t + P_i + \tau_t + \pi_k + (\epsilon_i + \eta_k + \zeta_t)$$

Here, Y_{ikt} is the outcome of patient i , with ECM provider k , at time t . ECM_i is an indicator that the patient is selected into the ECM treatment and $Post_t$ is an indicator that the ECM treatment period has started. Therefore β is the difference-in-difference coefficient of interest. P_i are a vector of patient-level controls, such as prior health care seeking, risk status, or health effects (in various models). τ_t are year fixed effects and π_k are provider controls or fixed effects. Standard errors are clustered with provider-year random effects indicated as $\eta_k + \zeta_t$.

For outcome (2), we specify the difference in means in the intervention year using the below specification:

$$Y_{kt} = \alpha + \beta(ECM_k \times Post_t) + \gamma_1 ECM_k + \gamma_2 Post_t + \tau_t + \pi_k + (\eta_k + \zeta_t)$$

Here, Y_{kt} is the outcome provider k , at time t . ECM_i is an indicator that the provider is selected into the ECM treatment and $Post_t$ is an indicator that the ECM treatment period has started. Therefore β is the difference-in-difference coefficient of interest. τ_t are year fixed effects and π_k are provider controls or fixed effects. Standard errors are clustered with provider-year random effects indicated as $\eta_k + \zeta_t$.

Funding statement

This project received funding from the Georgetown University McCourt School of Public Policy Massive Data Institute, the World Bank's Research Support Board, and the World Bank Strategic Impact Evaluation Fund.

Ethics

This study was approved by Harvard Longwood IRB protocol IRB20-114.

References

1. World Health Organization. Noncommunicable diseases: Progress monitor 2020. (2020).
2. World Bank. The state of health care integration in Estonia (2015).

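### The plan fixes no ECM dates or pre-period for its billing-data outcomes, and its difference-in-differences uses prior utilisation less efficiently than covariate adjustment would; the cost is precision, not bias

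*Combined protocol and SAP*

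**What the plan says.** Section 2.1.1 describes the billing data in the present tense: "We have electronic billing records spread over eight health care services categories", the last of them being "inpatient nursing care, and inpatient rehabilitation care over a 10 year period (2009 until 2019". It adds that "All the key outcomes of this study will utilize these systems of data". No other billing years are named anywhere.

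Section 2.4.1 says of the clinic randomisation blocks that "we used the QBS data and management scores for 2019". Section 2.2 (Clinic randomization) and section 2.3 (Patient randomization) then describe provider invitations, the loss of 47 providers, risk scoring of patients and patient randomisation, in that order. On the 47 providers, section 2.2 notes: "Since these providers dropped out of the program before the patient classification began".

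Section 2.3 (Outcomes) says the utilisation domain "measures the following indicators during the intervention year, at the patient level". Three primary outcomes sit in that domain and three in the acute-care domain.

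Section 2.4 (Statistical model) regresses the patient's outcome on ECM assignment, Post, and their product. Post "is an indicator that the ECM treatment period has started", and the coefficient on the product is the effect of interest. Earlier use of care appears only as an example of a patient-level control that some models may include, with no look-back period. No calendar date is given for the start of ECM, the intervention year or the pre-period.

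**The concern.** Blocks built from 2019 scores, followed by several further steps, place the start of ECM after 2019. The billing years named therefore hold no observation with Post = 1. A pre-analysis plan that does not say which years form Post = 0 leaves the baseline of six primary estimates to be chosen at analysis.

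The second issue is how the baseline is used. With the model as written, the estimate is the treated-minus-untreated difference in the intervention year, minus the same difference averaged over the pre-period. The old mean is subtracted with weight one, however well or poorly it predicts the intervention year. The pre-period may reach back to 2009, while the patients come from a list of people with multiple chronic illnesses that is updated each year. For some of them, early utilisation probably describes a time before the qualifying illnesses. The year just before ECM is likely to predict much better, yet it gets no special weight and may fall outside the pre-period.

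At stake is the precision of the six primary estimates, and the freedom to choose the baseline after outcomes are known.

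**Working it through.** **1. Calendar.** 2019 - 2009 = 10 reproduces the stated length of the billing window; counting both end years gives 11. I use 11 calendar years below.

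| Assumed ECM year | Named years inside it | Whole years between 2019 and it | Reach back to January 2009 |
|---|---|---|---|
| 2020 | 0 | 0 | 11 years |
| 2021 | 0 | 1 | 12 years |
| 2022 | 0 | 2 | 13 years |
| 2023 | 0 | 3 | 14 years |

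The ECM year is not in the documents. The protocol is dated April 2023, with enrolment complete.

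**2. Bias.** Apart from five providers whose patients were all assigned to ECM, patients were randomised within provider and risk stratum. Ageing and accrual of illness are common to both groups and do not bias the patient-level contrast. Only variance is compared from here on.

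**3. Variance model (all assumed).** The documents give no variance or correlation. Take equal variance (set to 1) in every year, for patients within a provider, and correlation at lag L of a + b x rho^L. Let w be equal weights over the pre-period years, V their correlation matrix, and c their correlations with the ECM year T. Then:

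- Intervention year alone: variance 1.
- Difference-in-differences: 1 + w'Vw - 2w'c.
- Adjusted contrast: 1 - k'S^-1 k. S is the covariance matrix of the two covariates (year T-1 and the 2009-2019 mean), and k holds their covariances with year T.

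**4. One setting in full:** (a, b, rho) = (0.1, 0.5, 0.8), T = 2022.

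- Pre-period 2009-2019: w'Vw = 0.3944, w'c = 0.2064, so 1 + 0.3944 - 2 x 0.2064 = 0.982.
- Pre-period 2009-2021: 0.874.
- Adjusted: k = (0.2064 for the mean, 0.5 for 2021); covariance of the two covariates 0.2330; determinant of S = 0.3944 - 0.2330^2 = 0.3401. So 1 - (0.2064^2 - 2 x 0.2064 x 0.5 x 0.2330 + 0.5^2 x 0.3944)/0.3401 = 0.726.
- Estimator: 0.874/0.726 = 1.20. Gap: 0.982/0.874 = 1.12. Total: 0.982/0.726 = 1.35.

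**5. All settings.** The last three columns are variance ratios, for T = 2021 / 2022.

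| (a, b, rho) | Lag-1 | Gap-free DiD vs adjusted | Gapped vs gap-free DiD | Gapped DiD vs adjusted |
|---|---|---|---|---|
| 0.1, 0.5, 0.8 | 0.50 | 1.21 / 1.20 | 1.07 / 1.12 | 1.29 / 1.35 |
| 0.2, 0.4, 0.8 | 0.52 | 1.16 / 1.15 | 1.06 / 1.11 | 1.23 / 1.28 |
| 0.3, 0.3, 0.8 | 0.54 | 1.11 / 1.10 | 1.05 / 1.10 | 1.17 / 1.20 |
| 0.1, 0.6, 0.7 | 0.52 | 1.28 / 1.28 | 1.08 / 1.13 | 1.38 / 1.45 |
| 0, 0.6, 0.85 | 0.51 | 1.25 / 1.25 | 1.07 / 1.13 | 1.34 / 1.42 |
| 0.4, 0.1, 0.7 | 0.47 | 1.02 / 1.01 | 1.02 / 1.04 | 1.05 / 1.05 |

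The ranges are 1.01-1.28 for the estimator, 1.02-1.13 for the gap and 1.05-1.45 for both. As effective loss of patients (1 - 1/ratio), the estimator alone costs about 1-22%, and both together about 4-31%. In 10 of the 12 cases the estimator accounts for the larger part, though in one of them the two parts are almost equal.

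**6. Sensitivity.**

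- ECM year 2020 (no whole missing year): total 1.02-1.28. ECM year 2023: total 1.06-1.50.
- 2009-2019 standard deviation at 0.7 of the later value: estimator 1.01-1.19, gap 1.02-1.12, total 1.05-1.33.
- An outcome uncorrelated from year to year: subtracting an 11-year mean gives 1 + 1/11 = 1.09, against 1 for the adjusted contrast.

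**7. Does the optional control help?** In a balanced panel fitted by least squares, a patient covariate that is constant over time and not interacted with Post is orthogonal to the ECM-by-Post product. It leaves the coefficient unchanged. Adding earlier use of care to the written model therefore does not deliver the gain in step 5.

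**The case against.** The strongest reply is that nothing is missing except dates. Section 2.1.1 describes records in hand and commits outcomes to the same data systems, not to that extract. The outcome and model sections presuppose intervention-year data. This stands. A reader might infer that the primary comparison cannot be run on the data described; the documents do not support that, because a later extract is evidently intended.

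A reader might also infer that the plan will add only the intervention year and pool 2009-2019 as the baseline. No section says so. The 5-45% figure therefore describes one possible choice of pre-period, and the billing window alone accounts for only 2-13%. The rest comes from choosing difference-in-differences over covariate adjustment.

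A third inference is that a baseline reaching back to 2009 in ageing patients biases the effect. Within-provider randomisation and the year effects rule that out for the patient-level contrast.

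Nor does difference-in-differences gain nothing over ignoring baseline. Even with the gap, its variance is 0.66 to 1.04 of the post-only value and exceeds 1 in only 2 of the 12 cases.

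Finally, the correlations are assumed, and equal yearly variance sits uneasily with illness that accrues over time. The 0.7 sensitivity narrows the range without removing it. The adjusted contrast had the lower variance in every setting tried.

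**Conclusion.** The concern holds as one of precision and specification. The named billing years precede ECM, on a strong inference from the 2019 blocking scores and the steps that followed. The plan leaves the ECM start, the extract end and the pre-period open. Its patient-level estimator is less efficient than the randomisation and the payer's records allow: about 1-28% higher variance with a gap-free pre-period, and 5-45% if 2020 onward were also left out. These sizes rest on the assumed correlations, equal yearly variance and an ECM year of 2021 or 2022. The low end applies when correlation barely decays with time. The finding concerns outcomes (1) and (3) only. It should be addressed, but it does not threaten the validity of the patient-level comparison.

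**What to change.** In section 2.4 (Statistical model), make the primary analysis of outcomes (1) and (3) the intervention-year contrast between ECM and non-ECM patients. In every primary model, adjust it for the patient's utilisation in the 12 months immediately before ECM start and for the patient's 2009-2019 mean, with provider and risk-stratum effects. Use the same start date for both patient groups of a provider. Keep difference-in-differences as a sensitivity analysis with its pre-period years listed. The section already introduces its model as an intervention-year difference in means, so the change is modest.

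In section 2.1.1, state the ECM start date and the dates of the intervention year, and commit to a gap-free extract from 2009 to the end of that year.

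The cost is a longer data request to the same payer, which must supply the intervention year anyway, and SAP wording. No patient contact is needed. One consequence to record: with provider effects, the five providers whose patients were all assigned to ECM contribute no treated-against-untreated contrast.
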